	,	Improved behaviours measured by the SDQ conduct problems sub-scale (Goodman, 2005)		
		Positive relationships/role models measured by the Peer relationships problem sub-scale in the SDQ (Goodman, 2005)		
	variable	Reduction in prevalence and variety of self-reported offending behaviours		

Baseline for primary outcome	measure (instrument, scale, source)	SRDS Variety Score
	variable	Improved pro-social values and behaviours Improved emotional symptoms Improved behaviours Positive relationships/role models
Baseline for secondary outcome	measure (instrument, scale, source)	Improved pro-social values and behaviours measured by the Strengths and Difficulties Questionnaire (SDQ) prosocial values sub-scale (Goodman, 2005) Improved emotional symptoms measured by the SDQ emotional symptoms sub-scale (Goodman, 2005) Improved behaviours measured by the SDQ conduct problems sub-scale (Goodman, 2005) Positive relationships/role models measured by the measured by the SDQ peer relationships problem subscale (Goodman, 2005)

Sample size calculations

Originally, we determined the final required participant sample size a priori, conducting Power Calculations in line with YEF guidance which suggested a total sample of 654 young people (327 per group) over the pilot trial and efficacy study would allow a statistically significant result to be identified (Power=0.80, two tailed, P<.05) for a reduction of involvement in offending of 11%. We recognised that to account for attrition STEER would need to recruit a greater number of young people to reach a final sample size of 654 by the end of the evaluation.

Our original approach was conservative and in line with Lipsey and Wilson (2001) who state that ½ d=r, which is in turn equivalent to the difference in proportions. Figure 2 shows that if we suggest that 30% of the young people that STEER does not work with commit violence compared to 20.5% of the young people that STEER does work with committing violence (equivalent to a Cohen's d=.19) a total sample of 654 (327 in each group) would be needed to detect a statistically significant result (Power=.80), in a two-tailed test (p<.05). This level of Cohen's d was selected because it is conservative and is about equivalent to a 10-11%

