difference which is in line with a weighted average effect size of mentoring programmes, based on comparisons of 18 studies in a meta-analysis of mentoring and offending using a random effects model (d=.21, 95% confidence interval .07 to .34) presented by Jolliffe and Farrington, 2008.³

Figure 2 presents the results of our power analysis at the protocol stage. It shows that in line with our conservative approach; we used a pre-test/post-test correlation of 0. This is because at the time we had no reason to believe based on data collected during the pilot trial that the variance would be different between the treatment and control group. However, we knew that inclusion of a pre-test as a covariate in impact analyses helps to explain (error) variance in the post-test and improves the likelihood of uncovering programme impacts by reducing the standard error of the impact estimate. It was difficult to estimate what the pre-test/post-test correlation would be as this depended on unknown sample characteristics and the characteristics of the measure under investigation (the SRDS when used in a sample similar to STEER, i.e., those who are known to have peers or family members involved in offending behaviour). The greater the estimated pre-test/post-test correlation the lower the MDES and the smaller the sample needed to detect this. In practice however, if the pre-test/post-test correlation changes from 0.0 to 0.4 the MDES for a sample size of 500 decreases from .25 to .23.

In line with good practice, we have conducted power analysis based on our final sample once all randomisation has been completed. This power analysis is based on the numbers involved in the trial at baseline. This is also presented in Figure 2. As part of this calculation, we have included a pre- post-test correlation of 0.5. This is based on values obtained from unpublished data from an RCT using the same outcome measure and in a similar population of adolescents (Humayun et al., 2019) which we discovered after our original power analysis for the protocol. It is also based on treating the SRDS variety score as a continuous variable in analysis as opposed to a dichotomous variable.

Our power analysis shows an MDES of 0.186 based on baseline data

SPSS 25 was used for calculations for the original protocol. PowerUp! (Dong, N. and Maynard, R. A., 2013) has been used for the calculations once all randomisation and baseline data had been completed.

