³ Please note that this rapid evidence assessment found that mentoring was more effective in reducing reoffending when contact between mentor and mentee was greater, in smaller scale studies, and when mentoring was combined with other services and interventions.

Figure 2: Sample size calculations

		Protocol	Randomisation
Minimum Detectable Effect Size (MDES)		0.19	0.186
Pre-test/ post-test correlations	Level 1 (participant)	0.0	0.5
	Level 2 (cluster)	N/A	N/A
Alpha		0.05	0.05
Power		0.8	0.8
One-sided or two-sided?		Two-sided	Two-sided
Number of participants by end of the trial	Intervention	327	337
	Control	327	349
	Total	654	686

Recruitment and baseline data collection was completed in October 2024. The cumulative T1 sample at the end of this period was 686.

337 young people were allocated to the intervention group, and 349 to the control group. This is broadly in line with the intended 1:1 allocation ratio. More information can be seen in Figure 3 below.

Referred into STEER = 1052 Eligible for STEER = Disengaged/became 997 ineligible= 316* Consented = Withdrew/excluded 694 from evaluation = 8 Baseline measures = 686 STEER= Signposting 337 = 349

Figure 3: Consort flow diagram for baseline data collection

Analysis

Overview

The following presents the analytical approach for the Efficacy Study. We currently do not know the structure of the complete data-set (for example, extent of or categories of missing data etc.) that we will receive as part of the Efficacy Study. This should be considered when interpreting the following analytical plan.

There is considerable debate about best practice when it comes to the analysis of data from RCTs. For example, Twisk et al. (2018) advocate for utilising longitudinal analysis of covariance or a repeated measures analysis without the treatment variable, but with the interaction between treatment and time in the model controlled. They argue that failure to control for baseline differences in outcomes between the groups can lead to biased estimates in the treatment. Alternatively, others have cautioned against this approach (e.g., Sen, 2013).

Based on our understanding of the literature our analysis will be conducted using General Linear Models controlling for baseline measurement of the outcome variable. An intention to treat approach will be used with all models unless otherwise stated. This in line with YEF Guidance (YEF, 2021).

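### Figure 2 labels the baseline sample of 686 as the end-of-trial number, so the MDES of 0.186 is a no-attrition best case set beside a post-attrition target

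*SAP*

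**What the plan says.** Under Sample size calculations, the SAP sets 654 (327 per arm) as the number needed at the end and recognises that "to account for attrition STEER would need to recruit a greater number of young people to reach a final sample size of 654". So 654 is a post-attrition target.

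The same section then describes a recalculation done after randomisation closed: "This power analysis is based on the numbers involved in the trial at baseline". On the correlation it says "we have included a pre- post-test correlation of 0.5", and on the result, "Our power analysis shows an MDES of 0.186 based on baseline data".

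Figure 2 shows both calculations side by side. In the row "Number of participants by end of the trial" the Protocol column gives 327/327/654 and the Randomisation column gives 337/349/686. The text below the figure identifies the second total: "The cumulative T1 sample at the end of this period was 686". Figure 3 also shows 686 as the number with baseline measures.

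No attrition rate, expected follow-up number or attrition-adjusted MDES appears anywhere in the SAP.

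**The concern.** One table row carries two different quantities. In the Protocol column it is a number hoped for at follow-up. In the Randomisation column it is a count taken before any follow-up. A reader comparing 0.19 on 654 with 0.186 on 686 would conclude that the trial finished larger than planned and slightly more sensitive. The table does not support that conclusion, because the second column makes no allowance for loss.

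The primary outcome is the SRDS score about six months after randomisation, so the sensitivity of the trial depends on how many participants supply that score. Version 1.2 of the SAP was issued specifically to update the power calculation and MDES, so 0.186 is likely to be carried forward as the trial's detectable effect. If follow-up is incomplete, that figure is too favourable.

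**Working it through.** **Inputs (SAP, Sample size calculations and Figure 2).** Two-sided alpha 0.05; power 0.80; pre/post correlation 0.5, so R² = 0.5² = 0.25; arms 337 and 349; continuous outcome; individual randomisation; no clustering.

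**Formula.** For an individually randomised trial with one baseline covariate,

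MDES = M × SE, with SE = √[(1 − R²)(1/n₁ + 1/n₂)] and M = t(0.975) + t(0.80) on N − 3 degrees of freedom.

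The normal approximation uses M = 1.960 + 0.842.

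**Reproducing the SAP's figure.** SE = √[0.75 × (1/337 + 1/349)] = 0.0661. MDES = 0.1856 with t quantiles and 0.1853 with normal quantiles, which matches 0.186. Other readings do not match: correlation 0 gives 0.214, R² = 0.5 gives 0.152, and a one-sided test gives 0.165. So 0.186 is the covariate-adjusted MDES with every one of the 686 analysed.

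**Room for loss.** Solving for the sample size at d = 0.186 by the normal approximation, n per arm = 2 × 0.75 × (1.960 + 0.842)² / 0.186², rounded up to 341, or 682 in total. That is 4 fewer than the 686 randomised. Keeping the SAP's own final target of 654 allows a loss of 1 − 654/686 = 4.7%.

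**With loss to follow-up.** The SAP gives no rate, so the rates below are assumptions. Loss is equal in both arms and the correlation stays at 0.5. Power is Φ(0.186/SE − 1.960).

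| Loss | Analysed | MDES | Power at 0.186 |
|---|---|---|---|
| 0% | 686 | 0.186 | 80% |
| 4.7% | 654 | 0.190 | 78% |
| 10% | 617 | 0.196 | 76% |
| 20% | 549 | 0.208 | 71% |
| 30% | 480 | 0.222 | 65% |

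**Against the SAP's benchmark.** The SAP justifies its effect size by a meta-analytic average for mentoring of d = 0.21. Detecting 0.21 with 80% power needs 2 × 0.75 × (1.960 + 0.842)² / 0.21², rounded up to 267 per arm, or 534 in total. That corresponds to a loss of 1 − 534/686 = 22%. Beyond about that point the MDES exceeds 0.21.

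**A coincidence to avoid.** The 0.190 obtained here for 654 equals the Protocol column's 0.19, but the two are not the same calculation. The Protocol column assumes a correlation of 0 and starts from a difference in proportions. The agreement does not put the columns on one basis.

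**The case against.** The strongest reply is that nothing is concealed. The text says twice that the calculation uses baseline data, the column is headed Randomisation, and the sentence below Figure 2 identifies 686 as the T1 sample. All of that stands. A reader might infer an arithmetic error or a hidden assumption, and the document supports neither: 0.186 is right for what the text says it is. The row label still says something else, and no figure allowing for loss is offered.

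A second reply is that the harm is unquantified. That also stands in part. It is tempting to say that the analysed sample does not deliver 80% power at 0.186, or that a null result will be misread against it. The SAP gives no retention, so the size of any shortfall cannot be established from it. Nor does the SAP say that results will be judged against 0.186; under Presentation of outcomes it commits to effect sizes with confidence intervals, which will reflect the numbers actually analysed.

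Third, the SAP states intention to treat and leaves missing-data handling open, so a complete-case analysis is not specified. This is fair. But the Missing data section goes no further than considering imputation of missing items, and commits to no method for an absent six-month questionnaire. It therefore gives no ground for treating all 686 as fully informative.

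Finally, because follow-up was due to end in May 2025 and this version is dated June 2025, a reader might infer that the six-month counts were already in hand. The document does not show that, and the Analysis overview says the structure of the complete data set was not yet known.

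**Conclusion.** The point holds as a fault of labelling and of an incomplete power statement. Figure 2 presents a baseline count as an end-of-trial number beside a post-attrition target, and the MDES of 0.186 is valid only as a best case with no loss to follow-up, which the SAP itself does not expect.

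The size depends on retention. It is small if the trial ends near its own target of 654 and becomes material at around 20 to 30% loss. These figures assume equal loss in both arms, a correlation of 0.5 among those followed up, and the baseline-adjusted model. The fault should be corrected, but it changes neither the design nor the analysis model and does not invalidate the trial.

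**What to change.** In Figure 2, relabel the 337/349/686 entries as the number randomised with baseline data, and mark 0.186 as the MDES assuming no attrition. Keep the end-of-trial label for the Protocol column's 654 only.

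Add the MDES at 95, 90, 80 and 70% retention (0.190, 0.196, 0.208 and 0.222), stating that these rates are assumptions.

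Once the number with a six-month SRDS score is known in each arm, quote the MDES for those numbers as the trial's detectable effect in place of 0.186. The first two changes need not wait for that count.

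The cost is a relabelled row, one added line or column, and a sentence. The stated detectable effect becomes slightly less favourable.

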[•] These are young people who disengaged or became ineligible because they: refused the service, had a parent who refused the service, moved out of area, were uncontactable, had too many services involved, or were deemed too complex due to an escalation in risk following the acceptance of referral.

The primary outcome for the evaluation of STEER is a reduction in prevalence of self-reported offending behaviours between baseline and six months as measured by the SRDS variety score.

The secondary outcomes that we are investigating are that young people receiving STEER compared to the business as usual (control) group have (See Figure 1 for more information about measures):

- A positive relationship with their mentor.
- Improved pro-social values and behaviours.
- Improved emotional symptoms.
- Improved behaviours
- Positive relationships/role models.

The General Linear Model will include the appropriate baseline outcome measure and the treatment dummy variable. For example, for the analysis of the primary outcome measure (SRDS Variety Score) the baseline SRDS variety score measure will be included and whether the individual received STEER or not

The purpose of these analyses is to estimate the difference between the STEER arm and the business-as-usual arm for each of the primary and secondary outcomes.

Variable transformation

It is possible that the baseline and outcome variables may be skewed. Skew will be assessed using the traditional criteria based on their distribution (i.e., skews of greater or equal to 1.0 or less than or equal to -1.0). Arguably, it is more desirable to use a generalised liner model (GLM) for the appropriate modelling of non-normally distributed variables (e.g., Akram et al., 2023), than it is to transform the data.

The analytic approach has been developed a priori and will be conducted with SPSS.

The syntax for all analysis will be provided once it has been developed after all data has been collected.

Primary outcome analysis

The primary outcome is a reduction in offending measured by the SRDS Variety Score. All young people will have completed the SRDS questionnaire before randomisation and again at around six months post-randomisation.

The SRDS Variety Score is measured on a scale from 0-19 with 0 indicating the young person has not reported any of the 19 forms of delinquency/offending behaviour and a score of 19 indicating that they have undertaken all forms of delinquency/offending behaviour.

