We will be using a General Linear Model, repeated measures design (assuming normality) or a generalized linear model, repeated measures design if the SRDS Variety score is nonnormally distributed. We will include a treatment by outcome interaction term in the analysis.

This analysis is designed to evaluate the differences in SRDS Variety Score between those in STEER and those who received business as usual (i.e. the control group).

This analysis will be conducted in SPSS.

Secondary outcomes analysis

Our approach to analysis of secondary outcomes will mirror the approach outlined above for the analysis of the primary outcomes. The secondary outcomes are:

- A positive relationship between the young person and mentor measured by the Social Support and Rejection Scale (SSRS).
- Improved pro-social values and behaviours measured by the SDQ pro-social values subscale.
- Improved emotional symptoms measured by the SDQ emotional symptoms subscale.
- Improved behaviour measured by the SDQ conduct problems subscale.
- An increase in positive relationships/role models measured by the measured by the SDQ peer relationships problem subscale.

All SDQ subscales contain 5 items and are measured on scales from 0 to 10. For the prosocial values subscale high scores are desirable (e.g., greater prosocial values), but for the other subscales (e.g., emotional symptoms subscale, conduct problems subscale, peer relationship subscale) high scores are not desirable (e.g., greater emotional problems, greater conduct problems, poorer peer relationships).

The SSRS has 4 dimensions; 'Feels valued', 'Trust', 'Mentoring', and 'Negativity'. Each item is scored from 1 (never) to 5 (always). Each subscale score is the average of items that make up the subscale. Higher scores on the negativity scale reflect higher levels of stress and negativity within the relationship. For the overall scoring of the scale a high score represents a positive relationship.

We will be using general linear models, repeated measures design (assuming normality) or generalized linear models, repeated measures design if the particular subscale is non-normally distributed. This will be determined once all data has been collected. We will include a treatment by outcome interaction term in the analysis.

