Analysis will be conducted using a General Linear Model, repeated measures design (assuming normality) or a Generalized Linear Model.

Interim analyses and stopping rules

As part of the pilot trial, we analysed the completeness, reliability and validity of outcomes questionnaires (including the measures of outcomes described above). We did this by conducting regular data quality audits including exploring: percentages of scale item completeness, scale means, standard deviations and skew as well as conducting Cronbach Alpha testing for scale reliability and correlation analysis to test theoretical validity. We will continue this approach for the duration of the Efficacy Study. Our interim analyses as part of the pilot trial did not, and will not, include a comparison between control group and treatment group data nor analyses of impact.

The trial will stop if Salford Foundation, YEF and Cordis Bright decide that STEER is unable to recruit a sufficient number of participants. Recruitment rates will be monitored against modelled targets regularly (monthly) and reviewed bi-monthly (at a minimum) as part of project group meetings. Any decision about stopping will be made in discussion with YEF and Salford Foundation colleagues.

The Salford Foundation project team will also be responsible for safeguarding of participants. They will report any serious adverse events overall and by trial arm. The trial will stop if Salford Foundation, YEF and Cordis Bright decide that STEER is unsafe for participants.

Longitudinal follow-up analyses

Other than assessing change in outcomes between baseline and follow-up as described above, there will be no other longitudinal follow-up analyses as part of the STEER evaluation.

Imbalance at baseline

We will produce a table of baseline descriptive characteristics for all young people before they were randomised and for those analysed. The baseline characteristics will include age, sex, ethnicity, and the relevant outcomes (SRDS Variety Score and SDQ subscales). We will report counts (including the numerator and denominator) and percentages in each category. Any differences will be discussed in the final evaluation report.

Missing data

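### The primary model adjusts only for baseline SRDS: a valid choice, but age, sex, ethnicity and baseline SDQ conduct problems could be added for a modest, assumed gain in precision

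*SAP*

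**What the plan says.** The SAP, Analysis, Overview, states: "The General Linear Model will include the appropriate baseline outcome measure and the treatment dummy variable". It illustrates this for the primary outcome: "the baseline SRDS variety score measure will be included and whether the individual received STEER or not". No other covariate is named for any model.

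The Primary outcome analysis section describes the model differently, as a repeated-measures general or generalised linear model, and adds: "We will include a treatment by outcome interaction term in the analysis". It names no covariates.

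Under Imbalance at baseline, the SAP lists what is held before randomisation: "The baseline characteristics will include age, sex, ethnicity, and the relevant outcomes (SRDS Variety Score and SDQ subscales"). Differences there are to be tabulated and discussed. Figure 1 records that there was no stratification.

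On power, Sample size calculations says "we have included a pre- post-test correlation of 0.5" and "Our power analysis shows an MDES of 0.186 based on baseline data". The numbers are given below Figure 2: "337 young people were allocated to the intervention group, and 349 to the control group".

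The Missing data section plans logistic regressions to find predictors of non-response. It does not say whether those predictors then enter the outcome model. The imputation it would consider concerns missing items.

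**The concern.** Sample size calculations itself argues that a baseline covariate absorbs residual variance and shrinks the standard error of the impact estimate. The plan applies that argument to one covariate and stops. Conduct problems at baseline, age, sex and ethnicity are plausible predictors of later self-reported offending, and they are already in the data set. Covariates fixed in advance that explain further variance would narrow the confidence interval without recruiting anyone. They would also take account of chance imbalance that the plan would otherwise only discuss. If some of them predict dropout differently in the two arms, they would remove a source of bias among those followed up. The stakes are modest: some precision, and some robustness to one form of selective loss.

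**Working it through.** **Inputs from the SAP.** 337 and 349 randomised (N = 686); pre-/post-test correlation 0.5, so R² = 0.5² = 0.25; two-sided alpha 0.05 and power 0.80 (Figure 2).

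**Inputs assumed.** Extra R² from the added covariates beyond baseline SRDS: 0 to 0.10. Loss to follow-up: 20% as an illustration, since the SAP gives no rate. About seven extra model terms.

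**Formula.** MDES = (t₀.₉₇₅ + t₀.₈₀) × √[(1 − R²)(1/337 + 1/349)].

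**The plan's figure.** 1/337 + 1/349 = 0.005833. With R² = 0.25 the root is √(0.75 × 0.005833) = 0.06614. On 683 degrees of freedom the MDES is 0.1856 (normal approximation 0.1853). The stated 0.186 is reproduced. With no covariate the MDES would be 0.214, so baseline SRDS already provides a substantial gain.

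**Adding covariates.** The standard-error ratio is √[(1 − R²)/0.75] and the equivalent sample size is 686 × 0.75/(1 − R²).

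| Extra R² (assumed) | R² | MDES | Reduction in SE | Power at 0.186 | Equivalent N | MDES with 20% loss |
|---|---|---|---|---|---|---|
| 0 | 0.25 | 0.186 | 0% | 80.3% | 686 | 0.2075 |
| 0.02 | 0.27 | 0.183 | 1.3% | 81.3% | 705 | 0.2048 |
| 0.05 | 0.30 | 0.179 | 3.4% | 82.9% | 735 | 0.2005 |
| 0.10 | 0.35 | 0.173 | 6.9% | 85.6% | 792 | 0.1932 |

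If the extra terms explain nothing, the lost degrees of freedom leave the MDES at 0.1856.

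**Selective loss.** An illustrative simulation used the trial's arm sizes, a true effect of zero, one added covariate with unique R² of 0.05, a log-odds slope of 0.7 for dropout and about 21 to 22% loss (1,500 repetitions). The mean estimate, in standard deviations of the outcome, was:

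| How dropout depends on the covariate | Baseline SRDS only | Covariate added |
|---|---|---|
| Equally in both arms | 0.000 | 0.000 |
| In one arm only | 0.032 | 0.000 |
| In opposite directions | 0.069 | 0.005 |

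The benefit therefore appears only when the relation between covariate and dropout differs by arm.

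**Baseline SSRS.** The Introduction says that data on every measure come from a survey at baseline and again at about six months. The baseline rows of Figure 1 and the list under Imbalance at baseline include SRDS and SDQ but not SSRS. The Overview needs a baseline value for each outcome, and Secondary outcomes analysis uses repeated measures for SSRS too. These passages do not agree on whether a baseline SSRS exists.

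**The case against.** The strongest reply is that nothing here is an error. With simple 1:1 randomisation and no stratification, the design requires no covariate, and adjusting for the baseline outcome alone gives a valid estimate and agrees with the stated MDES. That stands.

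The size of the gain is also assumed, and zero is a possible value. That stands too.

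Third, extra covariates are not automatically free. In a complete-case analysis, any missing value among them removes a participant, which could cancel a gain of 1 to 3% in the standard error. This stands unless a rule for missing baseline values is written in.

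Fourth, the choice between the Overview model and the repeated-measures model matters more than the covariate list, and the MDES formula applies to a linear baseline-adjusted model, not directly to a generalised one. This is right, and it is why the two edits belong together.

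Several stronger readings are tempting, but the SAP does not support them:

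- A reader might infer that the extra variables serve only a descriptive table. In fact baseline SDQ subscales are the baselines for the SDQ outcomes, ethnicity defines an exploratory subgroup, and the missingness models may draw on such variables. They are unused only in the primary model.
- A reader might infer that, without stratification, nothing balances these factors. Randomisation does so in expectation, and the standard error already allows for chance imbalance.
- A reader might infer that SSRS has no baseline. The Introduction says otherwise, so this is an inconsistency and not an established gap.
- A reader might infer general protection against dropout. Adjustment does nothing for loss driven by unmeasured factors or by the follow-up score itself, and the SAP shows no differential pattern.

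**Conclusion.** The point holds as a worthwhile improvement to a valid primary analysis, not as a correction of a wrong one. The plan's MDES of 0.186 is right for adjustment by baseline SRDS alone. Adding age, sex, ethnicity group and baseline SDQ conduct problems would bring it to between 0.186 and 0.173, on the assumption that together they add 0 to 0.10 to R² in a linear model. No stated figure in the SAP narrows that range, so it cannot be said that a definite amount of precision is being given up. The selective-loss argument is conditional: under the simulated settings, bias of about 0.03 to 0.07 SD was nearly all removed, but only where dropout related to the covariate differed by arm. Whether SSRS was measured at baseline is a separate inconsistency that has to be settled before the SSRS model can be written.

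**What to change.** Reconcile the Overview and the Primary outcome analysis section into one primary model. In the same dated amendment, and before arms are compared, specify it as six-month SRDS variety score on allocated arm, baseline SRDS, age, sex, ethnicity group and baseline SDQ conduct problems.

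State a simple rule for missing baseline covariates so that no participant is dropped, for example the pooled mean for a continuous covariate and a separate category for unrecorded ethnicity. Report the model with baseline SRDS alone as a sensitivity analysis.

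For each secondary outcome, use the same added covariates with that outcome's own baseline; for conduct problems that baseline is already in the set. For SSRS, first reconcile the Introduction with Figure 1 and Imbalance at baseline, and then state whether its model has a baseline term.

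The cost is a few degrees of freedom and one amendment. Version 1.2 is dated June 2025 and the Introduction expects completion in May 2025, so the amendment should record its date and confirm that no comparison between arms had been seen.
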